 803 applied and the fit of the models compared.

804 b. Analysis plan for PRO measures: Rasch analyses will be performed to calibrate
 805 both the VA LV VFQ-48 (completed by Vision Cohorts 1 and 2), PROMIS®-29,
 806 MRDQ (completed by all Vision Cohorts), ViSIO-PRO (completed by all Vision
 807 Cohorts), and the ULV-VFQ-50 (completed by Vision Cohort 3). Equivalence of
 808 different language versions will be established by calculating differential item
 809 functioning scores as part of the analyses. The scoring of each questionnaire will
 810 be completed according to the procedures for each instrument and is detailed
 811 further in a separate statistical analysis plan. Baseline scores will be cross-
 812 tabulated with categorical (severity of disease) versions of the outcome measures
 813 of interest at baseline. Changes in scores will be cross-tabulated with binary
 814 (progression of disease) versions of the outcome measures of interest at the 24
 815 and 48 month visits.

816 2. Investigate whether structural outcome measures can be validated as surrogates for
 817 functional outcomes in individuals with biallelic pathogenic mutations in the *EYS* gene

818 a. Analysis plan: Scatterplots and Spearman correlation coefficients of changes in
 819 SD-OCT EZ area versus VF progression from baseline to each visit will be
 820 evaluated. Repeated measures least squares models will be fit using VF
 821 progression as the dependent variable. Both linearity and the potential for larger
 822 variability with increasing EZ area will be evaluated, and transformations and/or
 823 higher order polynomial terms will be considered. Multivariate models using
 824 potential risk factors (as assessed below) for VF progression will be considered.

825 3. Evaluate possible risk factors (genotype, phenotype, environmental, and comorbidities)
 826 for progression of the outcome measures at 4 years in individuals with biallelic
 827 pathogenic mutations in the *EYS* gene

828 a. Analysis plan: The distribution of each outcome in terms of both absolute change
 829 and percent change from baseline to 4 years will be summarized (including
 830 tabulating categorically, as well as means, standard deviations, medians,
 831 quartiles), stratified by categorical levels of each potential risk factor of interest
 832 (listed below). The association of factors potentially related to change at 4 years
 833 for each outcome measure will be evaluated in univariate and multivariate
 834 analysis of covariance (ANCOVA) models (adjusting for baseline). A stepwise
 835 selection procedure will be used to build the final model. A threshold of $P < 0.10$
 836 will be used to add to the model, and a threshold of $P < 0.01$ will be used to remain
 837 in the multivariate model. Missing outcome data will be imputed using multiple
 838 imputation as noted in the primary analysis. Linearity of continuous factors will
 839 be assessed and possibly quadratic or cubic terms will be considered if non-linear.
 840 Secondary analyses using binary definitions of outcome measures will also be

- 841 explored in time to event analyses; Cox proportional hazard models will be
 842 evaluated using a parallel stepwise selection procedure.
- 843 • Potential risk factors to evaluate include:
 - 844 ○ Phenotypic:
 - 845 ▪ Clinical diagnosis
 - 846 ▪ Age of onset of initial vision symptoms
 - 847 ▪ Gender
 - 848 ▪ Race/ethnicity
 - 849 ▪ Visual acuity
 - 850 ▪ Lens Status (phakic/pseudophakic/aphakic)
 - 851 ▪ ERG 30 Hz flicker cone amplitudes b-wave (continuous)
 - 852 ▪ FAF pattern as measured qualitatively
 - 853
 - 854 ▪ SD-OCT (as factors related to SP Hill Of Vision (HOV))
 - 855 • Presence of cysts
 - 856 • Central subfield thickness
 - 857
 - 858 ▪ MP
 - 859 • Mean retinal sensitivity
 - 860
 - 861 ▪ SP (as factors related to SD-OCT EZ area)
 - 862 • Volume of 30 degrees HOV
 - 863 • Mean sensitivity
 - 864 • Full field HOV
 - 865 ○ Genotypic:
 - 866 ▪ Characterizations of the variants on the *EYS* protein
 - 867
 - 868 ○ Environmental factors
 - 869 ▪ Smoking status at baseline
 - 870 ▪ Vitamin A use at baseline
 - 871 ▪ Docosahexaenoic acid (DHA) use at baseline
 - 872 ▪ Lutein use at baseline
- 873 4. Evaluate variability of repeat perimetry testing and symmetry of left and right eye
 874 outcomes over 4 years in individuals with biallelic pathogenic mutations in the *EYS* gene
- 875 a. Analysis plan for variability of repeat perimetry testing at baseline: Scatterplots
 876 and Spearman correlation coefficients for pairs (first versus second) of testing
 877 values for each repeated perimetry test. Bland-Altman plots of the inter-eye
 878 difference versus the mean value will be inspected and a linear regression model
 879 for the differences will be used to test whether the slope is 0 and whether
 880 variability changes with greater mean values. The intraclass correlation
 881 coefficient of the values and the within-person variance will be estimated.

882 b. Analysis plan for the symmetry of left eye versus right eye: At baseline and each
883 subsequent testing time, the symmetry of the test result values from the left and
884 right eyes will be assessed and the symmetry of the change from baseline from the
885 left and right eyes will be assessed for each follow-up visit. Bland-Altman plots of
886 the inter-eye difference versus the mean value will be inspected and a linear
887 regression model for the differences will be used to test whether the intercept is 0
888 and the slope is 0. The intraclass correlation coefficient of the values will be
889 estimated.
890

891 **6.2.2 Sensitivity Analyses**

892 Analyses above will be repeated excluding cases that are not confirmed as pathogenic or likely
893 pathogenic by the Genetics Committee. This will confirm that the results are not influenced by
894 cases that may be ineligible based on genetics expert review but eligible based on clinical
895 review. Exclusions or subgroup analyses may be considered as a result of this analysis.
896

897 **6.2.3 Interim Data Analysis**

898 No formal interim analysis or “stopping guidelines” are planned for determining early stopping
899 according to statistical rules, as no intervention is being studied and thus early efficacy and
900 safety signals are not applicable.

901 Interim analyses will be planned for other reasons, including to evaluate data at baseline and
902 annual visits for reporting in preliminary manuscripts, as well as monitoring data for recruitment
903 and retention benchmarks, and quality assurance throughout the duration of the study. The FFB
904 Consortium Executive Committee will review and oversee these data and their use in reporting.

905

Chapter 7: Data Collection and Monitoring

906 7.1 Case Report Forms and Other Data Collection

907 The main study data are collected on electronic case report forms (eCRFs). When data are
908 directly collected in eCRFs, this will be considered the source data. For any data points for which
909 the eCRF is not considered source (e.g., lab results which are transcribed from a printed report
910 into the eCRF), the original source documentation must be maintained in the participant's study
911 chart or medical record. This source must be readily verifiable against the values entered into
912 eCRF. Even where all study data are directly entered into the eCRFs at office visits, evidence of
913 interaction with a live subject must be recorded (e.g., office note, visit record, etc.).

914 The Central Lab will generate genetic reports from the retinal dystrophy genetic panel testing
915 and/or family member testing analysis as applicable. These reports will be uploaded to the FFB
916 Consortium study website and made available to the clinical site.

917 The CGA will review the genetic lab report(s) submitted by the clinical site during genetic
918 screening against the genetic eCRF data to ensure that the data entered by the clinical site are
919 consistent with the source(s) provided prior to the Baseline visit. The CGA will document his/her
920 verification of these genetic data on the FFB Consortium study website and the clinical site will
921 be notified of the results of the review.

922 In addition to providing interpretation/evaluation of whether or not the *EYS* mutations are
923 causative of the disease on the FFB Consortium study website (see section 2.4.2), the Genetics
924 Committee will review and provide approval for the use of genetic reports from research labs to
925 be used for determining participant eligibility.

926 Reading Centers will conduct grading of the study data collected for MP, SD-OCT, SP and FAF
927 using the FFB Consortium study website. A Reading Center will conduct quality review only of
928 the first ERG obtained from each clinical site using the FFB Consortium study website. These
929 data will remain in the study database and will not be provided to the clinical site.

930 Each participating site will maintain appropriate medical and research records for this trial, in
931 compliance with International Council for Harmonisation of Technical Requirements for
932 Pharmaceuticals for Human Use (ICH) E6 and regulatory and institutional requirements for the
933 protection of confidentiality of participants.

934 7.2 Study Records Retention

935 Study documents should be retained for a minimum of six years from the date on which the CC
936 receives IRB approval to close the study. These documents should be retained for a longer
937 period, however, if required by local regulations. No records will be destroyed without the
938 written consent of the CC, if applicable. It is the responsibility of the CC to inform the
939 investigator when study documents no longer need to be retained.

940 7.3 Quality Assurance and Monitoring

941 Designated personnel from the CC will be responsible for maintaining quality assurance (QA)
942 and quality control (QC) systems to ensure that the clinical portion of the trial is conducted and
943 data are generated, documented and reported in compliance with the protocol, GCP and the

944 applicable regulatory requirements, as well as to ensure that the rights and wellbeing of trial
 945 participants are protected and that the reported trial data are accurate, complete, and verifiable.

946 Consistent with the Integrated Addendum to ICH E6 (R2)¹⁹, a risk-based monitoring (RBM) plan
 947 will be developed and revised as needed during the course of the study. This plan describes in
 948 detail who will conduct the monitoring, at what frequency monitoring will be done, at what level
 949 of detail monitoring will be performed, and the distribution of monitoring reports.

950 As much as possible, remote monitoring will be performed in real-time with on-site monitoring
 951 performed to evaluate the verity and completeness of the key site data. Elements of the RBM
 952 plan may include:

- 953 • Qualification assessment, training, and certification for sites and site personnel
- 954 • Oversight of IRB/EC coverage and informed consent procedures
- 955 • Central (remote) data monitoring: validation of data entry, data edits/audit trail, protocol
 956 review of entered data and edits, statistical monitoring, study closeout
- 957 • On-site monitoring (site visits): source data verification, site visit report
- 958 • Communications with site staff
- 959 • Participant retention and visit completion
- 960 • Quality control reports
- 961 • Management of noncompliance
- 962 • Documenting monitoring activities
- 963 • AE reporting

964 CC representatives or their designees may visit the study facilities at any time in order to
 965 maintain current and personal knowledge of the study through review of the records, comparison
 966 with source documents, observation and discussion of the conduct and progress of the study. The
 967 investigational site will provide direct access to all trial related sites, source data/documents, and
 968 reports for the purpose of monitoring and auditing by the sponsor, and inspection by local and
 969 regulatory authorities.

970 **7.4 Protocol Deviations**

971 A protocol deviation is any noncompliance with the clinical trial protocol, GCP, or procedure
 972 requirements. The noncompliance may be either on the part of the participant, the investigator,
 973 or the study site staff. As a result of deviations, corrective actions are to be developed by the site
 974 and implemented promptly.

975 The site PI and study staff delegated to study responsibilities are responsible for knowing and
 976 adhering to their IRB/EC requirements. Further details about the handling of protocol deviations
 977 will be included in the monitoring plan.

978

Chapter 8: Ethics/Protection of Human Participants

979 8.1 Ethical Standard

980 The investigator will ensure that this study is conducted in full conformity with Regulations for
981 the Protection of Human Participants of Research codified in 45 Code of Federal Regulations
982 (CFR) Part 46, 21 CFR Part 50, 21 CFR Part 56, and/or the ICH E6.

983 8.2 Institutional Review Boards and Ethics Committees

984 The protocol, ICF(s), recruitment materials, and all participant materials will be submitted to the
985 IRB or EC for review and approval. Approval of both the protocol and the ICF(s) must be
986 obtained before any participant is enrolled. Any amendment to the protocol will require review
987 and approval by the IRB or EC before the changes are implemented to the study. All changes to
988 the consent form will be IRB or EC approved; a determination will be made regarding whether
989 previously consented participants need to be re-consented.

990 8.3 Informed Consent Process

991 8.3.1 Consent Procedures and Documentation

992 Informed consent is a process that is initiated prior to the individual's agreeing to participate in
993 the study and continues throughout the individual's study participation. All consent forms will be
994 IRB-or EC- approved and in the case of written consent, the participant will be given the
995 opportunity to carefully read and review the document. For any form of consent presented
996 (written or verbal), the investigator or his/her designee (as approved by the IRB/EC) will explain
997 the research study to the participant and answer any questions that may arise. All participants
998 will receive a verbal explanation in terms suited to their comprehension of the purposes,
999 procedures, and potential risks of the study and of their rights as research participants. Extensive
1000 discussion of risks and possible benefits of participation will be provided to the participants and
1001 their families. Participants will be asked to carefully consider the consent form presented to
1002 them and have any questions answered prior to signing.

1003 Participants should have the opportunity to discuss the study with their surrogates or think about
1004 it prior to agreeing to participate. Participants must sign the ICF prior to any procedures being
1005 done specifically for the study. Participants may withdraw consent at any time throughout the
1006 course of the trial. A copy of the ICF will be given to participants for their records. The rights
1007 and welfare of participants will be protected by emphasizing to them that the quality of their
1008 medical care will not be adversely affected if they decline to participate in this study.

1009 8.3.2 Participant and Data Confidentiality

1010 Participant confidentiality is strictly held in trust by the participating investigators, their staff, the
1011 funder(s) and their agents. This confidentiality is extended to cover genetic tests in addition to
1012 the clinical information relating to participants. Therefore, the study protocol, documentation,
1013 data, and all other information generated will be held in strict confidence. No information
1014 concerning the study or the data will be released to any unauthorized third party without prior
1015 written approval of the sponsor.

1016 The CC, other authorized vendors or representatives of the funder, representatives of the
1017 IRBs/ECs, or regulatory agencies may inspect all documents and records required to be
1018 maintained by the investigator, including but not limited to medical records (office, clinic, or
1019 hospital) for the participants in this study. The clinical study site will permit access to such
1020 records.

1021 The study participant's contact information will be securely stored at each clinical site for
1022 internal use during the study. At the end of the study, all records will continue to be kept in a
1023 secure location for as long a period as dictated by the reviewing IRB/EC, institutional policies, or
1024 sponsor requirements.

1025 Study participant research data, which is for purposes of statistical analysis and scientific
1026 reporting, will be transmitted to and stored at the FFB Consortium CC, located at the Jaeb Center
1027 for Health Research in Tampa, Florida. This will not include the participant's contact or

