Endpoint	
Functional Outcomes:
 
 • VF sensitivity as measured by static perimetry with topographic analysis (Hill of Vision) and assessed by a central reading center • Early Treatment of Diabetic Retinopathy Study (ETDRS) Best corrected visual acuity (BCVA) letter score as measured on the Electronic Visual Acuity (EVA) system or ETDRS charts. Berkeley Rudimentary Vision Test (BRVT) will be used for patients unable to see letters • Mean retinal sensitivity as measured by fundus-guided microperimetry (MP) and assessed by a central reading center at selected sites with requisite equipment • Full-field retinal sensitivity as measured by full-field stimulus threshold (FST) testing to blue, white and red stimuli • Best corrected low luminance visual acuity (LLVA) letter score • Contrast sensitivity function (CSF) as measured by the CSV-1000E VectorVision chart • Retinal function using full-field electroretinogram (ERG) amplitudes and timing in response to rod- and cone-specific stimuli 
Structural Outcomes:
 
 • Ellipsoid zone (EZ) area as measured by spectral domain optical coherence tomography (SD-OCT) and assessed by a central reading center • Explore qualitative categorization of Fundus Autofluorescence (FAF) pattern as assessed by a central reading center • Explore quantitative measures of FAF as assessed by a central reading center 
Patient Reported Outcomes (PRO):
 
 • Vision Cohorts 1 and 2: Veterans Affairs Low Vision Visual Functioning Questionnaire (VA LV VFQ-48), Patient-Reported Outcomes Measurement Information System (PROMIS®-29), Michigan Retinal Degeneration Questionnaire (MRDQ) and Visual Symptom and Impact Outcomes Patient Reported Outcome (ViSIO-PRO) Instrument

ITEM	DESCRIPTION												

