- Baseline Visit date (defined as the start date of all Baseline testing) must be no later than 2 weeks after receiving confirmation of meeting **final study cohort criteria** from the CGA (and if possible, within 90 days of the Screening Visit date). All Baseline testing must be completed within 7 days of the Baseline Visit date, except PROs as specified
- All Follow up visit testing must be completed on the same day, except PROs as specified
- If ERG has been undetectable in the past, no need to perform at baseline, at investigator's discretion
- If ERG is undetectable at baseline, no need to perform at 48M, at investigator's discretion
- For static perimetry and microperimetry, all Vision Cohort 1 and 2 participants will complete two tests at baseline. The results will be compared according to the **visual field criteria** (section 3.2) to determine if a third test is needed.
- Kinetic VF III4e performed within the last 18 months prior to or including the Screening Visit date for Vision Cohort determination only
- Ophthalmic exam includes slit-lamp biomicroscopy, indirect ophthalmoscopy and intraocular pressure (IOP). IOP measurements will be taken prior to pupil dilation. Whenever possible the site should make its best effort to ensure that the exam takes place at approximately the same time of the day at each visit and with the same equipment
- PROs will be completed by participants who agree to answer these additional questions; may be completed in person or remotely any time within 6 months after Baseline or +/- 6 weeks of 24 or 48-month follow-up visits
- If the Baseline visit date is more than 90 days after the Screening Visit date, all Visual acuity procedures must also be completed

Visit Schedule for Vision Cohort 3

Visit	Screening	Baseline	12M	24M	36M	48M
Visit Target Windows	(up to Day -90) ^a	(Day 0) ^b	Wk 52 ± 4 (Phone call only)	Wk 104 ± 4 (Phone call only)	Wk 156 ± 4 (Phone call only)	Wk 208 ± 4 ^c
Participant-Level Procedures						
Informed Consent	X					
Demographics/Medical History (including pre-existing conditions, patient-reported daily activities and medications)	X					
Physical Exam (including height, weight and blood pressure)		X				
Concomitant Medications/Adverse Events		X	X	X	X	X
Patient Reported Outcomes (ULV-VFQ-50, PROMIS®-29, MRDQ and ViSIO-PRO) ^f		X				X
Ocular Procedures - All testing performed in each eye						
Complete Ophthalmic Exam ^e	X					X

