The most common phenotype reported in patients is a rod-cone dystrophy with relative central sparing.⁷ The average age of onset has been reported to be approximately twenty years with loss of visual acuity starting around age thirty. Most patients have non-recordable electroretinograms (ERGs) at the time of presentation, but patients may demonstrate some preservation on multifocal ERGs.⁷ Variation in autofluorescent patterns have been reported to correlate with severity of the disease. Some patients present with a crescent-shaped hyperautofluorescent ring with extension into the nasal/superior retina. This pattern has been associated with more mild disease and recordable ERGs.¹⁵ Posterior subcapsular cataracts are a common manifestation of this mutation and cystoid macular edema (CME) has a reported incidence of 31%.⁷

Retrospective studies have shown the rate of vision loss in *EYS* to be more severe than that of mutations caused by *USH2A*.¹⁶ Loss of visual acuity has been estimated to be 5.7% year with the median age for visual acuity to drop below 20/32 to be 36 years.¹⁶ The average rate of visual field (VF) loss has been estimated to be 23.1% per year and loss of ellipsoid zone (EZ) width to be 3-5% per year.^{5,16,17} To date, no large-scale prospective study of visual function has been conducted for patients with biallelic mutations in *EYS*. The Pro-EYS study will conduct a multicenter natural history study in patients with biallelic mutations in *EYS* with the purpose of better understanding disease progression as well as obtaining preliminary data for potential therapeutic trials in the future.

42 **1.2 Scientific Rationale for Study Design**

43 A prospective natural history study is the gold standard for tracking the course of disease. The
 44 knowledge of the course of patients with *EYS* mutations will guide the planning of future
 45 controlled treatment trials. Identifying the most sensitive and reliable outcome measures of
 46 retinal degeneration will greatly facilitate development of treatments with maximum efficiency.
 47 Together, these approaches are expected to have an impact on understanding *EYS*-related retinal
 48 degeneration, developing investigational treatment protocols, and assessing their effectiveness.

49 The goals and expected impact of this natural history study are to:

- 50 • Describe the natural history of retinal degeneration in patients with biallelic mutations in
- 51 the *EYS* gene

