FST	Diagnosys Espion (where available)	Does not need to be performed by study certified personnel*
Static Perimetry	Octopus 900 Pro (GATE Protocol)	Clinical site personnel certified for SP
Fundus-guided Microperimetry	MAIA (if available)	Clinical site personnel certified for MP
Kinetic Perimetry (historical)	Any equipment is acceptable	(Historical) Does not need to be performed by study certified personnel or recorded in the Pro-EYS Study Staff Delegation Log

* Personnel who will be performing procedure must be documented in the Pro-EYS Study Staff Delegation Log. The Principal Investigator (PI) is responsible for verifying individual qualifications and training specific to performing each type of procedure and ultimate accuracy and integrity of such data
		

495 **Chapter 4: Unanticipated Problem and Adverse Event Reporting**

496 **4.1 Unanticipated Problems**

497 Site investigators will promptly report to the CC all unanticipated problems meeting the criteria
 498 below. For this protocol, an unanticipated problem is an incident, experience, or outcome that
 499 meets all of the following criteria:

- 500 • Unexpected (in terms of nature, severity, or frequency) given (a) the research procedures
 501 that are described in the protocol related documents, such as the IRB/EC-approved
 502 research protocol and informed consent document; and (b) the characteristics of the
 503 subject population being studied
- 504 • Related or possibly related to participation in the research (possibly related means there is
 505 a reasonable possibility that the incident, experience, or outcome may have been caused
 506 by the procedures involved in the research)
- 507 • Suggests that the research places participants or others at a greater risk of harm than was
 508 previously known or recognized (including physical, psychological, economic, or social
 509 harm)

510 The CC also will report to the IRB all unanticipated problems not directly involving a specific
 511 site such as unanticipated problems that occur at the CC or at another participating entity such as
 512 a laboratory.

513 **4.2 Adverse Events**

514 **4.2.1 Definition**

515 Adverse Event (AE): Any untoward or unfavorable medical occurrence in a human subject,
 516 including any abnormal sign (for example, abnormal physical exam or laboratory finding),
 517 symptom, or disease, temporally associated with the subject’s participation in the research,

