- 745 • Natural history of 12 participants with *EYS* mutations (Miyata/Yoshimura, 2016)
- 746 ○ -5.2 ±3.1% for IS/OS extent

747 **Assumptions made:**

- 748 • Expect average annual decline in *EYS* to be 6.25% per year or 25% by 4 years
- 749 • True SD of percent change at 4 years similar to VPA 1-year SD of around 20%

750 **Based on these assumptions and the impact as presented above, a sample size for the**
 751 **combined Vision Cohorts 1 and 2 of 90 patients or 99 effective eyes has been selected.** With
 752 an effective sample size of 99, the half width of a 95% CI around the point estimate for percent
 753 change would be 4%. A comparison of two equal-sized subgroups would have about 80% power
 754 to conclude there is a difference if the true difference is 11%.

755 Based on the above justification, the total sample size will be 100 participants enrolled.
 756 Recruitment is anticipated to take 10 months from the time of study launch.

757 **6.1.4.1 Synopsis of Justification for All Outcomes**

758 The primary objective of the study is to characterize the natural history of retinal degeneration
 759 using the main outcome measures. Therefore, the precision of these estimates (how tight the CI
 760 is around the point estimate) for all of the outcomes of interest will be of the greatest importance
 761 in the consideration of sample size. With a sample size of 90 participants (effective sample size
 762 N= 99) for Vision Cohorts 1 and 2, all of these outcomes will have 95% CIs no wider than +/-
 763 4% (when analyzed in terms of percent change from baseline) if the SD is within 20%. Based on
 764 the available data, we expect the SD to be within 20%, which would yield CIs no wider than +/-
 765 4%. With an even smaller sample size of 65 participants (effective sample size N= 72), all of
 766 these outcomes will have 95% CIs no wider than +/- 5% if the SD is within 20%. This was
 767 considered acceptable precision to meet our objective for all outcomes of interest.

768 Furthermore, for the additional objective of evaluating risk factors associated with progression of
 769 these outcomes, a sample size of 90 (effective sample size N= 99) participants for Vision Cohorts
 770 1 and 2 will provide enough power to evaluate subgroups, especially those with close to equal
 771 distribution. For example, for 2 subgroups of equal size there will be at least 69% power to

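### Section 6.1.4.1 promises ±4% (±5% at 65 participants) for every outcome, but microperimetry and ERG are not planned in every Cohort 1/2 participant

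*Protocol*

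**What the plan says.** Section 6.1.4.1 takes 90 participants in Vision Cohorts 1 and 2, counted as 99 effective at a between-eye correlation of 0.8. It states that, if the SD of percent change is within 20%, "all of these outcomes will have 95% CIs no wider than" ±4%. A fallback sentence begins "With an even smaller sample size of 65 participants (effective sample size N= 72), all of" and gives the same outcomes ±5%. The precision is then "considered acceptable precision to meet our objective for all outcomes of interest". The 90 and the 65 are the enrolment goal and the enrolment minimum for Cohorts 1 and 2 combined (Section 2.1.1).

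Other parts of the protocol restrict who contributes to individual outcomes:

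- **Microperimetry:** the endpoint list in the Protocol Summary places it "at selected sites with requisite equipment".
- **ERG:** the footnotes to the Cohort 1/2 visit schedule say "If ERG has been undetectable in the past, no need to perform at baseline" and "If ERG is undetectable at baseline, no need to perform at 48M", both at the investigator's discretion. Section 1.1 reports "Most patients have non-recordable electroretinograms (ERGs) at the time of presentation".
- **FST and FAF:** the visit schedule and Section 3.4 tie both to device availability.
- **LLVA:** whether it is done depends on the visual acuity letter score (Section 2.3.2).
- **Questionnaires:** a schedule footnote limits them to participants who agree to complete them.

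**The concern.** The half-widths were worked out for an outcome observed in all 90 or all 65 enrolled participants, and are then asserted for every outcome. For microperimetry the design excludes participants at sites without the device. For ERG it allows the test to be skipped, and an undetectable baseline leaves no denominator for percent change, which is the metric behind ±4% and ±5%. Section 6.1 gives no outcome-specific N.

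One stated goal (Section 1.2) is to identify sensitive structural and functional measures for future trials. Someone comparing candidate endpoints is told that they share the same planned precision. For at least these two, the schedule does not support that.

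**Working it through.** **Inputs.** SD of percent change 20% (Section 6.1.4). Between-eye r = 0.8, so the multiplier is 2/(1 + r) = 1.11 (Section 6.1.1); the protocol's 90 → 99 corresponds to 1.1, which is used below. Two-sided 95% interval.

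**Formula.** Half-width = 1.96 × 20/√n (normal), or t(0.975, n − 1) × 20/√n, with n the effective sample size.

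**Step 1: the protocol's own figures.**

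- n = 99: 39.2/√99 = 3.94% (normal), 3.99% (t). Stated: 4%.
- n = 72: 39.2/√72 = 4.62% (normal), 4.70% (t). Stated: 5%.

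Both reproduce. Table 1 prints 5% for 50 participants (n = 55), where the formula gives 5.29% to 5.41%. The protocol therefore rounds to the nearest percent, and the thresholds below do the same.

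**Step 2: contributors needed for the stated precision.**

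- ±4% (half-width below 4.5%): n > (39.2/4.5)² = 75.9 (normal) or 78.3 (t). Dividing by 1.1 gives 69 to 72 participants, or 77–80% of 90.
- ±5% (below 5.5%): n > (39.2/5.5)² = 50.8 (normal) or 53.2 (t). Dividing by 1.1 gives 47 to 49 participants, which is 52–54% of 90 or 72–75% of 65.

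**Step 3: illustration.** The documents give neither the number of sites with microperimetry nor the share of participants with detectable ERG. The counts here are assumptions, at the same SD and r:

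| Contributors (assumed) | Effective n | Half-width, normal | Half-width, t |
|---|---|---|---|
| 45 | 49.5 | 5.57% | 5.71% |
| 30 | 33 | 6.82% | 7.09% |

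A lower correlation softens this. At r = 0.5, 45 participants count as 45 × 2/1.5 = 60 effective, giving 5.06% (normal) or 5.17% (t).

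**Step 4: the power figures in the same sections.** A two-sample t test with equal groups and two-sided alpha 0.05 gives 69.2% for a 10-point difference at n = 99 (stated 69%) and 55.3% at n = 72 (stated 55%). For 11 points at n = 99 it gives 77.3%, or 78.1% by the normal approximation (stated as about 80%). All of these count every enrolled participant as contributing at 4 years.

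**The case against.** Several points on the other side stand.

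- **The accepted standard is ±5%.** The acceptability sentence follows the 65-participant case. With 90 enrolled, an outcome measured in just over half of them still meets ±5%.
- **The statements are conditional.** Each is tied to a stated N and to SD within 20%. Table 1 goes down to 50 participants, and Section 6.1.2 invites its use for smaller groups. The text, however, never applies it to an outcome measured in a subset, and the acceptability sentence covers all outcomes.
- **Coverage is unknown.** A reader might infer from Section 1.1 that most of this cohort will have no usable ERG. The documents do not support that: the sentence is background literature, omission is discretionary, and about 70 of the 90 belong to Cohort 1, selected for better acuity and field. FAF is exploratory, and Spectralis is already the required SD-OCT device, so Spectralis FAF may be almost universal.
- **Imputation is planned.** Section 6.2.1 imputes missing time points. That helps with missed visits, but it cannot restore precision for participants who never had the test.

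It could also be said that the phrase means only the main outcomes. Section 1.4, however, names microperimetry, FAF and ERG among the procedures related to the primary outcomes.

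A reader might further infer that the power figures are wrong or should be cut for dropout. They are not wrong: 69% and 55% reproduce, about 80% for 77–78% is mild rounding, and r = 0.8 is stated in Section 6.1.1. No dropout rate is given. Modelling and a lower r would offset losses, while unequal subgroups, a larger SD or a higher r would add to them, so no attrition-adjusted figure can be offered as a bound.

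**Conclusion.** The claim for all outcomes is wrong as written. It holds for outcomes scheduled in every Cohort 1/2 participant. It is unsupported for microperimetry and ERG, and uncertain for FST, FAF, LLVA and the questionnaires. At SD 20% and r = 0.8, ±4% fails below about 69–72 contributors and ±5% below about 47–49. Whether any outcome falls below these counts cannot be settled from the protocol; the SD and r are themselves planning assumptions, with no ERG or microperimetry data behind them.

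This does not show that the study is too small or that its precision formula is faulty. The severity is minor: the fault is the scope of one justification, and the conduct of the study is unaffected.

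**What to change.** In Section 6.1.4.1, limit the ±4%/±5% statement to outcomes scheduled in every Cohort 1/2 participant: BCVA, EZ area, contrast sensitivity, and static perimetry subject to the follow-up waivers in Section 3.3.1. Give the expected N and half-width separately for microperimetry, ERG and FST, and for FAF, LLVA and the questionnaires where coverage is incomplete. Narrow the acceptability sentence to match.

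Optionally, add that the power figures of 69%, 77–78% (now given as about 80%) and 55% assume that all enrolled participants contribute at 4 years.

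The cost is a short rewording, a count of sites with the relevant devices, and an estimate of the share with detectable ERG. The downside is a less favourable stated precision for those outcomes. Enrolment and conduct do not change.
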